More than 5.7 million patients are admitted to intensive care units (ICU) each year in the United States.³⁷ The technologically advanced ICU is an unfamiliar frightening environment to patients and their families.¹ Critical

illness is a family crisis. There is strong evidence that family distress in response to critical illness does not disappear after ICU discharge.^{2,4,12,16} The Society of Critical Care Medicine³⁶ has identified a cluster of complications that occur in family members of ICU patients as Post Intensive Care Syndrome-Family (PICS-F). PICS in family members of adult ICU survivors includes symptoms of ongoing anxiety, depression, and post-traumatic stress disorder (PTSD). Data suggest that 70% of family members have symptoms of anxiety and 33% have symptoms of depression and PTSD, which can persist for \geq 4 years.^{7,9,13,24} Moreover, symptoms of anxiety, depression, and PTSD are higher and persist longer in family members than in adult ICU survivors.¹¹ Because PICS-F occurs with greater frequency in spouses and surrogate health decision-makers^{4,27,34} this study will focus on participants whom are spouses of mechanically ventilated critically ill adults (typically sedated and unable to make their own health decisions).

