- Symptoms of Anxiety and Depression. Anxiety is defined as worry or fear that does not go away and interferes with daily activities such as job performance, school work, and relationships.²³ Depression is defined as experiencing signs and symptoms most of the day, nearly every day, for at least two weeks.²³ The Hospital Anxiety and Depression (HAD) scale⁴² will be used to measure anxiety and depression at four time points: study day 1 (immediately prior to first intervention), study day 3, and by telephone interview at study day 30 and study day 90. The HADs is easy to administer and has been successfully used to measure symptoms of anxiety (7 questions) and depression (7 questions) in the general population and in family members of ICU patients.⁴ Scores for each subscale (anxiety and depression) range from 0 to 21 with scores categorized as follows: normal 0–7, mild 8–10, moderate 11–14, and severe 15–21. Although HADs was not designed to be a clinically diagnostic tool, in the event anxiety or depression subscales fall within the severe score range (15-21), the participant will be provided with a copy of their results and encouraged to follow up with their primary care provider for clinical evaluation.
- Symptoms of PTSD. Symptoms of PTSD will be quantified at four time points: study day 1, study day 3, and by telephone interview at study day 30 and study day 90, using the Impact of Event Scale (IES), which is the most commonly used instrument to measure symptoms of PTSD in PICS-F research.⁷ The IES has been widely used for many years and found reliable across a broad range of traumatic events.³⁹ The IES is not a tool for diagnosing PTSD, but instead detects symptoms indicating a risk of PTSD. Each of the 15 items is scored on a 6-point scale rated from 0 to 5; so that the total score can range from 0 to 75.¹⁵ Higher scores indicate more severe post-traumatic stress symptoms. In the event the total IES score is > 30, indicating a high risk of PTSD, the participant will be provided with a copy of their results and encouraged to follow up with their primary care provider for clinical evaluation.

Stress. Symptoms of stress will be quantified at four time points: study day 1 (immediately prior to first intervention), study day 3, and by telephone interview at study day 30 and study day 90, using Cohen's

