Data Management. Data will be downloaded into research electronic data capture (REDCap), a secure web application database, which will be accessed by a secure USF web connection with authentication and data logging. A unique identifier will be assigned to each participant by the PI in the database to conceal their identity on all research data. The data files will be backed up daily during the data entry process and once a week during other times by the PI. All data files will be housed on the university server, which is backed up every 24 hours and copies, are stored off-site for additional security. Access to the database will be password protected and limited to the investigators.

X. PLAN FOR CONTROL OF INVESTIGATIONAL DRUGS, DEVICES, AND BIOLOGICS N/A

XI. DATA ANALYSIS PLAN

Data Analysis

The defining parameter for feasibility is a minimum of two days participation in the study. Descriptive statistics will be reported as means +/- standard deviation for continuous variables and as frequencies and percentages for categorical variables. We will perform repeated measures models in order to compare symptoms of PICS-F conditions in the intervention and control groups. Specifically, the repeated outcome variables (symptoms of anxiety, depression, & PTSD) will be modeled using generalized linear mixed effects models to account for within-participant variations.³⁵ Estimates of treatment effects (differences between intervention and control groups) will be summarized with odds ratios and corresponding 95% confidence intervals. Our sample size of 10 participants is reasonable for a feasibility study and perform a power analysis for sample size and effect size for the larger dissertation study to follow. A timeline for the feasibility study is provided in Table 2.

Table 2

Timeline for Proposed Feasibility Study

| | Month | Month | Month | Month | Month | Month |
|----------|-------|-------|-------|-------|-------|-------|
| Activity | 1 | 2 | 3 | 4 | 5 | 6 |

| Participant Recruitment & Enrollment | | | |
|---|--|--|--|
| Participant 1 and 3 month follow up | | | |
| Data collection | | | |
| Data management | | | |
| Analysis of final results | | | |
| Prepare dissertation study | | | |
| Final results manuscript | | | |

XII. DATA AND SAFETY MONITORING

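### Treatment effects on the HADS and IES scores are reported only as odds ratios with no stated outcome form, and no model-based mean difference or variance is planned for sizing the next study

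*Combined protocol and SAP*

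**What the plan says.** Section XI (Data Analysis) says that the repeated symptom outcomes (anxiety, depression, PTSD) "will be modeled using generalized linear mixed effects models to account for within-participant variations", and then that "Estimates of treatment effects (differences between intervention and control groups) will be summarized with odds ratios and corresponding 95% confidence intervals". No other between-group measure is named. There is no distribution, link function, cut-off or cumulative (ordinal) model, and no statement whether the estimate is pooled over visits or given by visit.

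Section IX (Key Variables and Their Measurement) defines the outcomes as numeric scores. For the HADS, "Scores for each subscale (anxiety and depression) range from 0 to 21"; for the IES, items are summed "so that the total score can range from 0 to 75". The same section lists four HADS bands (0-7, 8-10, 11-14, 15-21) and an IES value: "In the event the total IES score is > 30", the participant receives the results and is advised to seek evaluation. The severe HADS band has the same use. Nothing says that a band or the IES value defines the analysed outcome.

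Section VI makes determining the effect size part of the primary aim. Section XI says the sample of ten is reasonable for feasibility and to "perform a power analysis for sample size and effect size for the larger dissertation study to follow". On summaries, it says "Descriptive statistics will be reported as means +/- standard deviation for continuous variables", without saying whether these are by arm and by visit.

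**The concern.** An odds ratio has meaning only once the event, or the ordered scale, behind it is fixed. Here the same data could give an odds ratio for HADS of 8 or more, 11 or more, or 15 or more, or for a shift across the four bands, at one visit or over all of them. The choice would be made after the data are seen.

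The consequence falls on the study that this one is meant to size. The documents do not state that study's endpoint. If it is a score, the inputs are a mean difference, an SD and a within-person correlation, and section XI plans to report none of these from the model. If it is binary, the inputs are the arm proportions at a named cut-off, and none is named. As written, the one planned effect estimate serves neither case.

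**Working it through.** **Plan's own figure.** The sample of 10 (5 per arm) comes with no power calculation, so there is nothing to reproduce. The checks below show what the missing definition could cost. Inputs from the documents are 5 v 5 (section IX), the score ranges and HADS bands (section IX), and the symptom rates in section VII: "Data suggest that 70% of family members have symptoms of anxiety and 33% have symptoms of depression and PTSD". Everything else is an assumption and is marked so.

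**1. Does the definition change the next study's size?** Assume normal HADS subscale scores with means 10 v 8 and SD 4, and 80% power at two-sided 0.05.
- Mean difference: n per arm = 2(1.96+0.842)²(4/2)² = 62.8, so 63.
- Binary: n per arm = [1.96√(2p̄(1−p̄)) + 0.842√(p₁(1−p₁)+p₂(1−p₂))]² / (p₁−p₂)².

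| Outcome | Control v intervention | OR | n per arm, SD 4 | n per arm, SD 3 to 5 |
|---|---|---|---|---|
| Mean difference | 10 v 8 | – | 63 | 36 to 99 |
| Score ≥8 | 0.734 v 0.550 | 0.442 | 106 | 63 to 161 |
| Score ≥11 | 0.450 v 0.266 | 0.442 | 106 | 63 to 161 |
| Score ≥15 | 0.130 v 0.052 | 0.367 | 212 | 212 to 248 |

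**2. Information kept if a normal score is dichotomised.** Relative efficiency = φ(z)²/[p(1−p)], where z is the normal quantile at prevalence p.
- p = 0.33: 0.3621²/0.2211 = 0.593
- p = 0.50: 0.3989²/0.25 = 0.637
- p = 0.70: 0.3477²/0.21 = 0.576

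The loss over 33-70% prevalence is therefore 1−0.637 to 1−0.576, or about 36-42%.

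**3. Can a pooled binary odds ratio be estimated at 5 v 5?** Assume that the section VII rates are the control rates, unchanged or halved in the intervention arm; complete data at days 3, 30 and 90; and a latent normal score with common within-person correlation ρ. Let A and B be the probabilities that one person is yes at all three visits, or no at all three. An arm of n people is all-yes or all-no with probability f = Aⁿ + Bⁿ, and the trial is affected with probability 1−(1−f₁)(1−f₂).

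Example, 0.33 v 0.165 at ρ = 0.5. Control: A = 0.119, B = 0.432, so f₁ = 0.015. Intervention: A = 0.036, B = 0.667, so f₂ = 0.132. Result: 1 − 0.985×0.868 = 0.145.

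| Control v intervention | ρ = 0.5 | ρ = 0.9 |
|---|---|---|
| 0.33 v 0.33 | 0.029 | 0.119 |
| 0.70 v 0.70 | 0.046 | 0.156 |
| 0.33 v 0.165 | 0.146 | 0.307 |
| 0.70 v 0.35 | 0.034 | 0.126 |

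The table is from 400,000 simulated trials; numerical integration agrees to within 0.002.

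**4. What a mean difference would achieve.** For a single-visit, baseline-adjusted comparison at 5 v 5 (7 df), the expected 95% half-width in SD units is t(0.975, 7) × √(1−r²) × E[√(2/5 + d²/Sxx)] × 0.965. Here r is the assumed correlation with the day-1 score, d is the chance baseline difference between arms, and Sxx is the within-arm baseline sum of squares. With t = 2.365 and the expectation 0.679:
- r = 0.5: 2.365×0.866×0.679×0.965 = 1.34 SD
- r = 0.7: 2.365×0.714×0.679×0.965 = 1.11 SD
- r = 0.9: 2.365×0.436×0.679×0.965 = 0.68 SD

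**The case against.** The strongest reply is that this is only an unstated outcome form. An odds ratio is itself an effect size, so it does not contradict the aim. The documents also lean partly towards caseness: section VII describes the syndrome by percentages with symptoms, and section IX sorts HADS scores into bands. An ordinal or binary odds ratio may well be intended. Descriptive means and SDs are planned, the scores will be in the database, and at ten participants no scale gives a dependable effect size.

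Much of this stands. A reader might infer that the plan will dichotomise the scores; it does not say so, and every figure in steps 2 and 3 depends on that assumption. A reader might also infer that the odds ratio would often be inestimable. For a single-visit binary odds ratio, 1−[1−p₁⁵−(1−p₁)⁵][1−p₂⁵−(1−p₂)⁵] does give 26-49% at 5 v 5. But section XI specifies repeated-measures models, so the pooled 3-31% is the relevant range. An ordinal model would be expected to fail less often still: with the four HADS bands, one visit, 5 v 5 and normal scores (assumed SD 3 to 5), the arms separate in about 3-6% of trials at means 10 v 10 and 6-13% at 10 v 8. The section VII rates are also for family members in general, with no threshold given, whereas this trial enrols spouses and excludes those being treated for these conditions.

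The reply does not supply the missing definition. The bands offer three thresholds and an ordinal reading, and the plan selects none. Descriptive means allow at most a crude difference, and only if they are given by arm and visit. They provide neither baseline adjustment nor the within-person correlation.

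**Conclusion.** The point holds in this form: the only planned treatment-effect summary is an odds ratio whose outcome is undefined, and no model-based mean difference, SD or within-person correlation is planned although determining effect size is part of the primary aim. That much rests on the text alone.

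The size is conditional. If the scores are dichotomised, 36-42% of the information in a normal score is lost at 33-70% prevalence. A pooled odds ratio at 5 v 5 then has an all-yes or all-no arm in 3-15% of trials (ρ = 0.5) or 12-31% (ρ = 0.9), with the section VII rates taken as control rates and the intervention rate unchanged or halved.

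Two stronger conclusions are not supported. The documents do not show that an odds ratio is an invalid effect measure here. Nor would a mean difference make this study's effect size reliable: its half-width is still about 0.7-1.3 SD, and that figure is for a single-visit comparison, not for the mixed model recommended below, whose precision was not evaluated. What improves is definition, efficiency and estimability. The trial can proceed, but the wording should be settled before any outcome data are analysed.

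**What to change.** Replace the odds-ratio sentence in section XI with text such as:

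> HADS-Anxiety, HADS-Depression and IES total scores will be analysed as continuous outcomes in linear mixed models adjusted for the day-1 score, with small-sample t-based intervals (for example Kenward-Roger). Treatment effects will be given as mean differences with 95% confidence intervals at days 3, 30 and 90, together with the between-participant SD and the within-person correlation. HADS bands and IES above 30 will be reported as n/N per arm and visit. With five participants per arm all estimates are imprecise. The power analysis will show sample sizes over a range of mean differences and over the confidence interval of the SD.

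The expected half-width of about 0.7-1.3 SD for a single-visit adjusted difference, with its assumed baseline correlations of 0.9 to 0.5, can be quoted beside the statement on imprecision.

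If the investigators prefer to keep an odds ratio, the plan should name the model (cumulative-logit or binary), the cut-off, and whether the estimate is pooled or by visit, and should report the mean difference alongside it.

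The cost is wording only: no new data or visits. The downside is the loss of a headline odds ratio for caseness, but the n/N tables would still supply the inputs if the dissertation study takes a binary endpoint.

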Since the project involves minimal risk and will be conducted at a single site, data and safety monitoring will be conducted by the study PI, [name] and reviewed with USF faculty advisor/co-investigator [name] on a bi-weekly basis. The review of data and safety monitoring will include all study processes, protocol compliance with inclusion/exclusion criteria, sex and minority enrollments, and safety of participants, including but not limited to review of adverse events.

XIII. Multi-center Studies

N/A

XIV. Involvement of non-USF institutions/sites (domestic and foreign) $N\!/\!A$

XV. Involvement of Independent Investigators N/A

XVI. HUMAN PARTICIPANTS INSTRUCTIONS

Recruitment and Informed Consent. The PI will make daily rounds to the adult ICUs and speak with the charge nurses regarding availability of the spouse of patients intubated and admitted within the last 36 hours, and are expected to stay in the ICU for at least 36 hours. The bedside nurse will approach the potential participant to ask if they would like to be approached by the PI with an invitation to enroll in the study. The potential participant will be provided with an oral explanation of the nature of the study and study information in writing. The information will include all elements required for informed consent, and will include all pertinent contact information as well as information about withdrawal from the study. Written consent will be obtained. If at any time the participant does not wish to continue to participate in the study, no additional interactions with the participant will take place, no follow-up data will be collected, and that participant's data forms will be destroyed. The study PI has extensive experience in obtaining consents from family members of critically ill adults. The PI will work closely with the staff of the Burn Center, Cardiac Care, Cardiothoracic Surgery, Medical, Medical Surgical, Neuro Science, Surgical Trauma, and Vascular Surgery ICUs, the nurse managers, and medical directors to ensure that all eligible spouses of patients have an equal opportunity for inclusion.

Characteristics. Participants will be recruited from spouses of the inpatient population at TGH, which has 1,080 licensed acute care beds served. Characteristics of inpatients at TGH are presented in Table 3. Patients in the study units are representative of the hospital wide patient characteristics in relation to gender and ethnic background.

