| Characteristics | Hillsborough County, FL | Hospital (inpatient | |
|-------------------------------|---|---------------------|--|
| Gender | A CONTRACTOR CONTRACTOR AND A | | |
| Male | 48.7% | 43.9% | |
| Female | 51.3% | 56.1% | |
| Ethnic category | | | |
| Hispanic or Latino | 26.5% | 22.8% | |
| Not Hispanic or Latino | 73.5% | 77.2% | |
| Racial category | | | |
| American Indian/Alaska Native | 0.6% | 0.6% | |
| Asian | 4.0% | 0.6% | |
| Native Hawaiian/Pac Islander | 0.1% | 0.1% | |
| Black / African American | 17.5% | 20.8% | |
| White | 75.3% | 73.8% | |
| More than 2/ Other / Unknown | 2.5% | 4.1% | |

Table 3. Characteristics of Study Population, Geographic Area and Hospital (2014 data)

Sources of Materials. Data will be obtained from the participant's verbal feedback, wrist actigraphy, and health assessment instruments. Data will include age, race, ethnicity, sex, marital status, history of PICS conditions, level of education, distance of hospital commute, Perceived Stress Scores, Hospital and Anxiety Scores, Impact Event Scores, and NIH Toolbox Emotion Battery Score. Each participant will be assigned an arbitrary study identification number to conceal their identity, and no individually identifiable private information will be entered into the study database.

Potential Risks. The risks of participation in the study are minimal. Risks include skin irritation from the actiwatch, as well as apprehension with the Perceived Stress Scale, Hospital Anxiety and Depression Scale, Impact Event Scale, and NIH Toolbox Emotion Battery health assessments.

There is no alternative therapy. However, participants may elect not to participate and may withdraw from the study at any time without affecting the care they or the patient receives.

Protections Against Risk. The SĀF-T intervention will be administered in the privacy of the ICU's consultation room to avoid interference with critical care procedures for the patient. At all times, we will place the patient's need for medical treatment, and avoidance with interference with treatment, foremost.

The information obtained will be kept strictly confidential, protecting the identity of participants in all reports or publications that may result from this research. Each participant will be assigned an arbitrary code number to conceal their identity on all research data, and all research data will be maintained in locked file cabinets under the direct supervision of the PI and USF faculty advisor.

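### Active withdrawal triggers automatic destruction of the participant's data forms, which can remove the evidence a 10-person feasibility study needs about the people who leave

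*Combined protocol and SAP*

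**What the plan says.** The rule is in Section XVI, Recruitment and Informed Consent. Its trigger is broad: "If at any time the participant does not wish to continue to participate in the study". Three things then follow: contact ends, no later follow-up is collected, "and that participant's data forms will be destroyed". No condition is attached and the participant need not ask for deletion. Assessments run to Day 90, so the rule applies until then. It covers active withdrawal only. A missed telephone interview, the patient's death or early ICU discharge is not named as a trigger.

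Section XI sets the feasibility criterion: "The defining parameter for feasibility is a minimum of two days participation in the study". It plans to analyse the symptom scores with "generalized linear mixed effects models to account for within-participant variations". It gives no denominator for feasibility, no analysis set and no rule for missing data.

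Data are also held away from any form. Section IX, Data Management, places them in REDCap and on a university server, "which is backed up every 24 hours and copies, are stored off-site for additional security". Section XVI, Sources of Materials, lists "wrist actigraphy, and health assessment instruments" among the sources. Protections Against Risk refers both to locked cabinets and to password-protected computers. None of these sections says what happens to a withdrawn participant's data.

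On oversight, Section XII states: "The review of data and safety monitoring will include all study processes". It goes on to name eligibility compliance, sex and minority enrolment, and safety. Withdrawals are not named.

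**The concern.** People who choose to leave are central evidence in a feasibility study. Section VI makes adherence to the protocol part of the primary aim, Section XI defines feasibility by two days of participation, and the Publication and Presentation Plans promise results on longitudinal follow-up. Section VI also says the findings will be used to design the dissertation study.

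A rule that destroys forms at withdrawal works against all of these aims. It can remove the record of when someone left and whether two days were completed. It can also remove baseline and any Day 3 or Day 30 scores. A mixed model can use scores from people with incomplete follow-up, but only if those scores still exist. With five participants per arm, one person is 20% of an arm.

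Ending contact with someone who leaves is not in question. The concern is only the automatic loss of what they had already given.

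**Working it through.** The plan states no figure that can be reproduced here: the sample size of 10 is given without a formula or a dropout rate. The check therefore sets out what the rule removes, what can be recovered, and how far the feasibility rate could move.

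**What survives a withdrawal**

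| Item | Source outside the data forms | Recoverable? |
|---|---|---|
| Number randomised, and arm | Assignment envelopes (Section IX); consent forms (Section XVI, Protections Against Risk); enrolment review (Sections XII and XVI) | Yes, in principle |
| Day of withdrawal | None planned; the Section XII review might notice it | Not assured |
| Two days completed | None planned | Not assured |
| Baseline, Day 3 and Day 30 scores | REDCap, if entered and kept | Not stated |
| Actigraphy | Device record, if kept | Not stated |

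**Scores at stake, if held only on the forms.** Assessments fall on Days 1, 3, 30 and 90. Withdrawal after baseline but before Day 3 loses 1 collected assessment. Withdrawal between Days 3 and 30 loses 2, and between Days 30 and 90 it loses 3.

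**Two-day participation rate.** Inputs: 10 randomised (Section IX, Sample). The documents give no withdrawal rate, so 1 to 3 active withdrawals is an assumption. For scale, the chance of at least one withdrawal in 10 is 1 − (1 − p)^10, which is 40%, 65%, 89% and 97% for assumed p of 5%, 10%, 20% and 30%.

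Let *e* be withdrawals before two days, *l* withdrawals after two days, and *f* participants who do not withdraw but still fall short of two days.

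- True rate = (10 − e − f)/10
- Surviving forms only = (10 − e − l − f)/(10 − e − l)
- Over 10, with withdrawn participants' records lost = (10 − e − l − f)/10

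With f = 0, so that every other participant meets two days:

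| e | l | True (exact 95% CI) | Surviving forms | Over 10, records lost |
|---|---|---|---|---|
| 1 | 0 | 9/10 (55–99.7%) | 9/9 = 100% | 9/10 |
| 2 | 0 | 8/10 (44–97%) | 8/8 = 100% | 8/10 |
| 3 | 0 | 7/10 (35–93%) | 7/7 = 100% | 7/10 |
| 0 | 1 | 10/10 (69–100%) | 9/9 = 100% | 9/10 |
| 0 | 2 | 10/10 (69–100%) | 8/8 = 100% | 8/10 |
| 0 | 3 | 10/10 (69–100%) | 7/7 = 100% | 7/10 |
| 1 | 1 | 9/10 (55–99.7%) | 8/8 = 100% | 8/10 |

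Intervals are Clopper-Pearson.

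**Relaxing f = 0.** Eligibility needs an expected ICU stay of only 36 hours, or 1.5 days, and the ICU phase ends at discharge if that comes within 3 days. Some non-withdrawers may therefore fall short. With e = 1, l = 0, f = 1, the true rate is 8/10 = 80% and surviving forms give 8/9 = 89%. With e = 2, l = 0, f = 1, they are 7/10 = 70% and 7/8 = 87.5%. The surviving-forms figure is then below 100% but still too high when withdrawals are early.

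**The case against.** Automatic destruction can be defended as a deliberate protection for distressed spouses in a minimal-risk study, so changing it is a trade-off and not the correction of a mistake. That is fair as far as it goes. The change proposed below still ends contact and keeps deletion available on request.

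A second objection is that in a single-site study of 10 the investigator will know how many were randomised. This stands for the head count, and it makes a rate computed only from surviving forms less likely. A head count does not show the day someone left, whether two days were met, or what they scored.

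Third, the scores may be safe in REDCap, and actigraphy is a device record. This also stands in part. The clause names only data forms, while Protections Against Risk speaks of research data in locked cabinets, which suggests that paper forms exist. Whether the scores would survive electronically cannot be settled from the protocol. The consent pages were removed from our copy and may address it; the protocol says participants receive information about withdrawal.

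Three stronger readings are tempting, and the documents support none of them. A reader might infer that the plan drops withdrawn participants from the denominator; it is silent on the denominator, so the 100% figures show what could happen under one computation and are not a stated rule. A reader might infer that all electronic data are erased; the text does not say so. A reader might also infer that the treatment-effect estimate would be biased or materially less precise; nothing in the documents allows that to be shown, and no such claim is made.

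**Conclusion.** The point holds in a limited form. As written, active withdrawal at any time up to Day 90 leads to destruction of that participant's data forms without any request, and this works against the study's own feasibility aims. Confidence is high on the clause itself and on the absence of a planned withdrawal log or stated denominator in the protocol text. It is medium on whether REDCap, backup and actigraphy data are left uncovered, because the consent pages may say.

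The possible error in the two-day rate runs in either direction. On the illustrative assumptions (1 to 3 active withdrawals, everyone else meeting two days) it is 10 to 30 percentage points: too high if withdrawals are early and only surviving forms are counted, too low if withdrawals are late and records are lost over a denominator of 10. The first of these shrinks if other participants also fall short. The size depends wholly on the assumed number and timing of withdrawals. This is a cheap improvement to make before a withdrawal occurs, since destroyed records cannot be rebuilt.

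**What to change.** Replace the destruction clause with wording such as:

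> Data collected up to withdrawal are kept and analysed by assigned group unless the participant asks for deletion. Arm, day of withdrawal and any volunteered reason are logged for every randomised participant. All randomised participants are the denominator for feasibility.

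State that the rule covers paper forms, REDCap records and actigraphy files, and say how backups are treated. State that after a deletion request a de-identified log line (arm and day only) remains, so that the denominator is preserved. Contact still ends at withdrawal. Repeat the denominator in Section XI next to the two-day criterion.

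The cost is a change to the protocol and consent wording, an IRB amendment, and one log line per participant. The real downside is that the default moves from destruction to retention, so protection then depends on the participant knowing that deletion can be requested; the consent wording must say so plainly. Participants who have already consented keep the terms they agreed to unless they are re-consented.
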